8.3.3.5.2. ACQ-5 Score

The ACQ-5 is a five-item questionnaire which has been developed as a measure of the subject's asthma control that can be quickly and easily completed (Juniper, 2005). The response options for each of these questions consists of a zero (no impairment/limitation) to 6 (total impairment/limitation) scale with the total score ranging from 0 to 30. ACQ-5 score is the average of the 5 non-missing items and will be calculated at each visit for each subject. The MCID is 0.5 points. ACQ-5 will be conducted only in subjects who reported a diagnosis of asthma at the Screening visit.

Change from baseline to Week 16 in ACQ-5 score will be analyzed using an ANCOVA model without MI. The ANCOVA model will be analogous to the model described in [Section 8.3.1.3](#),

and will include covariates for treatment group, region (United States, Eastern Europe), and baseline ACQ-5 score. Actual and change from baseline values in ACQ-5 score will be descriptively summarized by visit using as observed data.

ACQ-5 scores will also be presented in a by-subject data listing.

8.3.3.5.3. PK Concentrations

GB001 plasma concentrations will be summarized by visit/timepoint using the following descriptive statistics: number of subjects with non-missing data, arithmetic mean, SD, arithmetic % coefficient of variation (CV), geometric mean, geometric % CV, median, minimum, and maximum.

For calculation of mean concentrations, all below limit of quantification (BLQ) values will be set to zero. If the number of values that are BLQ at a nominal timepoint exceed 50% of the observations collected at that nominal timepoint, summary statistics for the timepoint will not be calculated. If the mean concentration value is less than the lower limit of quantification (LLOQ) value, then the mean, median, minimum, and maximum concentration values will be set to BLQ.

GB001 plasma concentrations will also be presented in a by-subject data listing.

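### The SAP's PK display rule prints the maximum as BLQ (and usually the median too) when the mean is below LLOQ, although its own 50% rule guarantees that at least half the samples were quantifiable

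*SAP*

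**What the plan says.** SAP section 8.3.3.5.3 (PK Concentrations) asks for these statistics at each visit and timepoint, besides the number of subjects: "arithmetic mean, SD, arithmetic % coefficient of variation (CV), geometric mean, geometric % CV, median, minimum, and maximum". Three rules then deal with BLQ samples:

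1. Substitution: "For calculation of mean concentrations, all below limit of quantification (BLQ) values will be set to zero".
2. Suppression: if BLQ values "exceed 50% of the observations collected at that nominal timepoint, summary statistics for the timepoint will not be calculated".
3. Overwrite: the trigger is a calculated mean under LLOQ, and the instruction for that case is "then the mean, median, minimum, and maximum concentration values will be set to BLQ".

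The section makes no exception for a median or maximum that is itself quantifiable. It closes by saying that "GB001 plasma concentrations will also be presented in a by-subject data listing". Plasma concentration is an exploratory endpoint (SAP section 2.1; Protocol section 3).

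**The concern.** The overwrite judges four statistics by the value of one of them. The mean is pulled down by the zeros; the maximum is not affected by them at all, and the median is affected only once the zeros reach the middle of the ordered sample. The suppression rule has already removed every timepoint at which most samples are BLQ. What remains is a set of timepoints at which the overwrite can replace a measured maximum, and often a measured median, with a label saying it was not measurable. At stake is the accuracy of those entries in the PK summary table.

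**Working it through.** The plan states no figure to reproduce here, so the check is on the logic of the rules.

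**Inputs.** From SAP section 8.3.3.5.3: BLQ counts as 0 for the mean; statistics are suppressed above 50% BLQ; the overwrite is triggered by mean < LLOQ. Assumptions: quantifiable means at or above LLOQ, and BLQ also counts as 0 when the median is taken. LLOQ is not given, so results are in units of LLOQ; the argument does not depend on scale.

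**Notation.** n samples, b of them BLQ, p = b/n, and q = mean of the n - b quantifiable values.

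**When the overwrite acts**
- A mean must have been calculated, so b <= n/2.
- The mean is (1 - p) x q. It is below LLOQ only if q < LLOQ/(1 - p).
- If p = 0, every value is at or above LLOQ and so is the mean. Hence 0 < p <= 50%.
- The ceiling on q is 1/0.90 = 1.11 x LLOQ at p = 10%, 1/0.80 = 1.25 at 20%, 1/0.60 = 1.67 at 40%, and 1/0.50 = 2.0 at 50%.

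**What is then true of each statistic**
- Maximum: n - b >= n/2 samples are quantifiable, so the maximum is at or above LLOQ. Printing BLQ is always false.
- Median, b < n/2: the middle position (or both middle positions) lies among the quantifiable values, so the median is at or above LLOQ. Printing BLQ is false.
- Median, b = n/2: the median is (0 + smallest quantifiable value)/2. The smallest quantifiable value is at most q, and q < 2 x LLOQ, so the median is below LLOQ. Printing BLQ is correct.
- Minimum: p > 0 means at least one sample is BLQ. Printing BLQ is correct.
- Mean: below LLOQ by the trigger itself. Printing BLQ is correct.

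**Examples (illustrative values, units of LLOQ)**

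| Samples | Mean | Median | Maximum | Table shows |
|---|---|---|---|---|
| n = 20: 9 BLQ, 11 evenly spaced from 1.0 to 2.2 | 11 x 1.6/20 = 0.88 | (1.0 + 1.12)/2 = 1.06 | 2.2 | BLQ for all three |
| n = 42: 20 BLQ, 20 at 1.2, 2 at 2.0 | (24 + 4)/42 = 0.67 | 1.2 | 2.0 | BLQ for all three |
| n = 50: 25 BLQ, 24 at 1.0, 1 at 25.9 | (24 + 25.9)/50 = 0.998 | (0 + 1.0)/2 = 0.5 | 25.9 | BLQ for all three |

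The third row shows that the hidden maximum need not be close to LLOQ. It also shows the one case (exactly half BLQ) in which BLQ is right for the median.

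**Numerical confirmation.** The rules were coded and run on 400,000 simulated timepoints (n from 5 to 50, lognormal concentrations). The overwrite acted 14,881 times. The maximum was at or above LLOQ in all 14,881, and the minimum was truly BLQ in all 14,881. The median was at or above LLOQ in 11,912 of the 11,912 with fewer than half BLQ, and in 0 of the 2,969 with exactly half BLQ. The share of simulated timepoints at which the overwrite acted reflects the simulation settings and says nothing about this trial.

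**The case against.** The case for leaving the sentence alone is that little follows from it, and most of that case stands.

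- The individual concentrations are in the by-subject listing. A reader might infer that the rule conceals which subjects were exposed. The documents do not support that: a summary table never identifies subjects, and the listing does. Nor would a summarised row imply that nobody had measurable drug, since the 50% rule means at least half did.
- A reader might infer that mixed adherence is enough to trigger the overwrite. It is not. If 45% of samples were BLQ and the rest averaged 10 x LLOQ (illustrative), the mean would be 0.55 x 10 = 5.5 x LLOQ and nothing would be overwritten. The quantifiable values must also average close to LLOQ, and nothing in the documents says they would. Adherence is in any case assessed from tablet counts (SAP section 7.2).
- A reader might infer that the geometric mean and geometric CV, which the overwrite does not name, would contradict the BLQ entries. The SAP gives no separate BLQ rule for them, so what they would show is unspecified; with zeros in the data, the geometric mean would be zero or undefined.
- The SAP plans no test, model or decision rule on plasma concentration. The objectives relating PD markers and pharmacogenetics to outcome are outside this SAP (SAP section 1).

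These points limit the importance of the flaw. They do not rescue the rule, because there is no data set in which its entry for the maximum is true. The one situation in which a BLQ maximum would be correct, every sample BLQ, has already been suppressed.

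**Conclusion.** The rule is wrong as written, at low importance. Whenever the overwrite acts, the maximum is misreported; the median is misreported as well when fewer than 50% of values are BLQ. The mean, the minimum, and the median at exactly 50% BLQ are labelled correctly. The result for the maximum rests only on the SAP's own rules and on quantifiable meaning at or above LLOQ. The statement about the median at exactly 50% also assumes that zero is substituted there.

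How often this would happen cannot be derived, because neither document gives the assay LLOQ or expected concentrations. It may be rare, or may never happen. The damage is confined to a descriptive table for an exploratory endpoint, and no efficacy or safety inference changes.

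**What to change.** Replace the overwrite sentence in SAP section 8.3.3.5.3 with a rule that judges each statistic on its own value: show the mean, median and minimum as BLQ only if that statistic is itself below LLOQ, and always show the maximum as observed. No exception is needed for the maximum, because timepoints with more than 50% BLQ are not summarised. In the n = 42 example the row would then read mean BLQ, median 1.2 x LLOQ, minimum BLQ, maximum 2.0 x LLOQ.

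The cost is one SAP sentence and a small edit to the PK table program. No new data are needed.

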8.4. Examination of Subgroups

8.4.1. Examination of CRSsNP and CRSwNP Subgroups

Subgroup analyses of the primary and three secondary efficacy endpoints (i.e. change from baseline to Week 16 in SNOT-22 total score, Lund-Mackay score, AM NC score, and AM TSS) will be performed using the primary analysis approach (which is based on the amount of missing data as described in [Table 1](#)) for the randomized CRSsNP and CRSwNP subgroups. The CRSwNP subgroup will be further broken down based on the presence or absence of comorbid asthma (CRSwNPsA and CRSwNPwA).

Models used for the subgroup analyses will be similar to those used for the primary and secondary efficacy endpoints as specified in [Sections 8.3.1](#) and [8.3.2.1](#), with the following additional covariates: treatment group by disease status stratification factor values used for randomization (referred to as ‘strata’ henceforth in this section, for brevity) interaction, strata by visit interaction, and treatment group by strata by visit interaction for SNOT-22 total score, AM NC score, and AM TSS score; and treatment group by strata interaction for Lund-Mackay score. For SNOT-22 total score, AM NC score, and AM TSS, if the model does not converge, a reduced model excluding region, baseline score, and baseline score by visit interaction will be used. For Lund-Mackay, if the model does not converge, a reduced model including only treatment group, strata, and treatment group by strata interaction will be used.

Heterogeneity of treatment effect across the CRSsNP and CRSwNP subgroups (CRSsNP, CRSwNP, CRSwNPsA, CRSwNPwA) will be evaluated by presenting interaction p-values for the treatment group by strata by visit interaction for Week 16 for SNOT-22 total score, AM NC score and AM TSS score, and treatment group by strata interaction for Lund-Mackay score. The

interaction term will be used to test whether the treatment effects in the CRSsNP and CRSwNP subgroups are significantly different, using CRSsNP as the reference subgroup. Additionally, the interaction term will be used to test whether the treatment effects in CRSwNPsA and CRSwNPwA are significantly different, using CRSwNPsA as the reference group.

Actual, change from baseline, and percent change from baseline values in SNOT-22 domain scores will be descriptively summarized by visit for the randomized CRSsNP and CRSwNP subgroups using as observed data.

8.4.2. Examination of Other Subgroups

Subgroup analyses of the primary and three secondary efficacy endpoints (i.e. change from baseline to Week 16 in SNOT-22 total score, NPS, AM NC score, and AM TSS) will be performed using the primary analysis approach (which is based on the amount of missing data as described in [Table 1](#)) for all of the subgroups specified below. For any subgroup level that does not comprise $\geq 20\%$ of the ITT population, the SNOT-22 total score, AM NC score, and AM TSS analyses based on the models will not be performed. For any subgroup level that does not comprise $\geq 20\%$ of subjects in the ITT population with nasal polyps, the NPS analyses based on the models will not be performed. The subgroups of interest are described below.

Demographic characteristic subgroups:

- Age (years; $< 50, \geq 50$)
- Sex (male, female)
- BMI (kg/m^2 ; $< 30, \geq 30$)
- Region (United States, Eastern Europe)

Baseline disease characteristic and atopic/allergic condition subgroups:

- SNOT-22 total score at Baseline ($\leq \text{Median}, > \text{Median}$, where median is based on the ITT population) for the SNOT-22 total score endpoint
- NPS at Baseline ($\leq 6, > 6$) for the NPS endpoint
- AM NC score at Baseline ($\leq \text{Median}, > \text{Median}$, where median is based on the ITT population) for the AM NC score endpoint
- AM TSS score at Baseline ($\leq \text{Median}, > \text{Median}$, where median is based on the ITT population) for the AM TSS score endpoint
- Prior NP surgery (yes, no)
- Allergic Rhinitis (seasonal and/or perennial) at Baseline (yes, no)

Biomarker baseline characteristic subgroups:

- Blood eosinophils at Baseline ($10^9/\text{L}; < 0.25, \geq 0.25$)
- FeNO at Baseline (ppb; $< 25, \geq 25$)

- Chloride at Baseline (mmol/L; \leq Quartile 1, $>$ Quartile 1- \leq Quartile 2, $>$ Quartile 3- \leq Quartile 3, $>$ Quartile 3, where quartiles are based on the ITT population)

Models used for the subgroup analyses will be similar to those used for the primary and secondary efficacy endpoints as specified in [Sections 8.3.1](#) and [8.3.2.1](#), with the following additional covariates: subgroup (if different than the aforementioned covariates, i.e. region), treatment group by subgroup interaction, subgroup by visit interaction, and treatment group by subgroup by visit interaction. If the model does not converge, a reduced model excluding strata, region (if not the subgroup), baseline score, and baseline score by visit interaction will be used.

Heterogeneity of treatment effect across different levels of each subgroup will be evaluated by presenting interaction p-values for the treatment group by subgroup by visit interaction for Week 16. The interaction term tests whether the treatment effect is significantly different across different levels of the subgroup (between males and females, for example). The least severe or lower subgroup level (where applicable) will be used as the reference subgroup, and the test will assess whether the treatment effect in the more severe level(s) or higher value level(s) differs from that in the reference subgroup. For subgroups without directionality (sex and region), male and United States, respectively, will be used as the reference subgroup.

Forest plots of the treatment effect estimates, corresponding 95% CIs, subgroup p-values, and interaction p-values for the subgroup analyses described in [Sections 8.4.1](#) and [8.4.2](#) will be provided.

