2.5. Sample Size Determination

A total sample size of approximately 100 subjects (approximately 50 per treatment group, randomized in a 1:1 ratio) is estimated to provide approximately 90% power to detect a treatment difference of 12.0 between GB001 and placebo at a 0.050 two-sided level of significance for the primary endpoint of change from baseline to Week 16 in SNOT-22 score, assuming a common standard deviation (SD) of 16.8 and a dropout rate of 15% using a two-sided t-test.

A total sample size of approximately 64 subjects in the CRSwNP stratum (approximately 32 per treatment group, randomized in a 1:1 ratio) is estimated to provide approximately 80% power to detect a treatment difference of 1.3 between GB001 and placebo at a 0.050 two-sided level of significance for the secondary endpoint of change from baseline to Week 16 in NPS, assuming a common SD of 1.7 and a dropout rate of 15% using a two-sided t-test.

Therefore, the total sample size of approximately 100 subjects overall will consist of approximately 64 subjects in the CRSwNP stratum and 36 subjects in the CRSsNP stratum.

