8.3. Analysis Methods

8.3.1. Primary Efficacy Analyses

The primary endpoint is the change from baseline to Week 16 in SNOT-22 total score.

SNOT-22 is a validated questionnaire to assess the impact of CRS on quality of life (QOL) and utilizes a 2-week recall period. It is a 22-item outcome measure on a 5-point category scale applicable to sinonasal conditions and surgical treatments. The questionnaire consists of 22 items across 5 domains: Nasal, Ear, Sleep, General and Practical, and Emotional. A scale ranging from 0 (no problem) to 5 (problem as bad as it can be) is used to respond to each item in the questionnaire. The total scores range from 0 to 110 with higher total scores implying greater impact of CRS on QOL. A Minimal Clinically Important Difference (MCID) is available: 8.90 ([Hopkins, 2009](#)).

Total and domain scores will be derived by taking the sum of the non-missing item responses at each visit.

If the number of subjects overall with a missing change from baseline to Week 16 SNOT-22 total score is < 10%:

- The primary analysis will be mixed-effects model with repeated measures (MMRM) without multiple imputation (MI).
- As a sensitivity analysis, analysis of covariance (ANCOVA) without MI will also be performed.

If the number of subjects overall with a missing change from baseline to Week 16 SNOT-22 total score is $\geq 10\%$:

- The primary analysis will be MMRM with MI.
- As sensitivity analyses, MMRM without MI and ANCOVA with MI will also be performed.

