8.3.1.2. MMRM with MI

Missing SNOT-22 total scores at post-baseline visits will be imputed using an MI approach. Missing SNOT-22 total scores at baseline will not be imputed.

The following steps will be performed:

- Step 1: Intermittent missing values will be imputed using the Markov Chain Monte Carlo (MCMC) method ([Schafer, 1997](#)), using a noninformative prior (Jeffreys) for the prior information for the means and covariances and expectation-maximization (EM) for the initial mean and covariance estimates.
- Step 2: Monotone missing values will then be imputed using a linear regression model ([Allison, 2005](#)) including the imputed intermittent missing values in step 1. A monotone missing pattern is such that in the event that a variable is missing it is implied that all subsequent variables are also missing (e.g., once a subject withdraws from study, no additional data is expected for that subject).
- For each step, MI will be performed within each treatment group with covariates for disease status stratification factor values used for randomization (CRSwNP with

comorbid asthma, CRSwNP without comorbid asthma, and CRSsNP), region (United States, Eastern Europe), and non-missing values for baseline SNOT-22 total score and Weeks 4, 8, 12, and 16 SNOT-22 total scores. Should convergence issues occur due to small cell size for the categorical covariates at either step, the categorical variable(s) causing convergence issues will be removed from the model.

- Missing change from baseline and percent change from baseline in SNOT-22 total scores will be computed from the imputed SNOT-22 total scores.
- The analysis of the primary endpoint as described in [Section 8.3.1](#) will be performed for each complete, imputed dataset.
- For step 1, fifty imputations will be performed. For step 2, 1 imputation will be performed if 50 imputations were performed for step 1. Fifty imputations will be performed for step 2 if step 1 was skipped (e.g., for assessments only collected once post-baseline or for endpoints without intermittent missing values).
- Results of the MMRM on the multiple imputed data sets will be combined to generate an overall estimate and associated variance using Rubin's rules ([Rubin, 1987](#)).

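### When 10% or more of Week 16 values are missing, SAP 8.4.2 tests eight subgroup interactions on data imputed without the subgroup variable, which pulls each interaction toward zero and makes its test conservative

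*SAP*

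**What the plan says.** SAP 8.4.2 covers SNOT-22 total score, NPS, AM nasal congestion and AM total symptom score. It says that the subgroup analyses "will be performed using the primary analysis approach (which is based on the amount of missing data as described in" Table 1). SAP 8.3.1 sets the switch at 10% missing change from baseline to Week 16. At or above that level it states: "The primary analysis will be MMRM with MI". Below it, MMRM is run without imputation.

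SAP 8.3.1.2 defines the imputation model: "For each step, MI will be performed within each treatment group with covariates for disease status stratification factor values used for randomization", together with region, the baseline score and the scores at Weeks 4, 8, 12 and 16. SAP 8.3.2.1.2 adds only the Week 20 value, for nasal congestion and total symptom score.

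For each endpoint, 8.4.2 lists ten subgroup variables. Two are in the imputation model: region and the endpoint's own baseline score. Eight are not: age, sex, BMI, prior polyp surgery, allergic rhinitis, blood eosinophils, FeNO and chloride. SAP 8.4.2 adds subgroup terms to the analysis model, including treatment by subgroup by visit, and reports interaction p-values and forest plots. No subgroup-specific imputation is described. The added treatment terms cannot be read as part of the imputation, because that is run separately in each arm.

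**The concern.** The analysis model estimates a treatment-by-subgroup effect that the imputation model leaves out. Within an arm, a missing Week 16 value is drawn from a regression that does not distinguish, say, high from low FeNO. The draw reflects the subgroup only as far as that subject's earlier scores already do. Two results follow. The estimated interaction is pulled toward zero. In addition, Rubin's variance exceeds the true sampling variance of the shrunken estimate, so the test rejects too seldom.

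At stake are the interaction p-values and subgroup rows in the forest plots. A reader could take them as evidence that the effect does not vary by eosinophils or FeNO, when part of that uniformity comes from the imputation.

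**Working it through.** **Plan's own figures.** SAP 2.5 plans for "approximately 90% power to detect a treatment difference of 12.0 between GB001 and placebo at a 0.050 two-sided level of significance", "assuming a common standard deviation (SD) of 16.8 and a dropout rate of 15% using a two-sided t-test". With n per arm = 2(1.960 + 1.282)² × (16.8/12.0)² = 41.2, this rounds up to 42, and 42/0.85 = 49.4, or 50 per arm. Noncentral-t power at 42.5 completers per arm is 0.902. For NPS (difference 1.3, SD 1.7, 80% power), n = 2(1.960 + 0.842)² × (1.7/1.3)² = 26.8, or 27, and 27/0.85 = 31.8, or 32 per arm; power is 0.790. Both figures reproduce. The SAP gives no figure for the subgroup analyses.

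**Does the switch apply?** The plan's 15% dropout exceeds the 10% threshold, so under its own assumption the subgroup models run on imputed data.

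**Simulation.** There were 1,500 trials per scenario.
- From the SAP: 100 subjects at 1:1; 50 imputations by sequential regression within arm on strata, region, baseline and prior visits; Rubin's rules; SD 16.8.
- Assumed: a 50:50 subgroup, true interaction 12, between-visit correlation 0.6, and dropout that is monotone and completely at random.
- Simplification: the analysis was a Week 16 ANCOVA with treatment by subgroup, standing in for the MMRM.

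Shrinkage is 1 minus (mean with SAP imputation / mean with no data missing, same trials). Signs are dropped. Results at 15% missing:

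| Dropout timing | Mean, no missing | Mean, SAP imputation | Shrinkage | Rubin SE / sampling SD | Coverage | Power, SAP | Power, subgroup added |
|---|---|---|---|---|---|---|---|
| All after Week 12 | 11.84 | 11.63 | 2% | 7.38/6.82 = 1.08 | 96.9% | 33.9% | 34.8% |
| Spread over visits | 12.10 | 11.37 | 6% | 7.53/6.69 = 1.13 | 97.2% | 29.8% | 35.3% |
| All before Week 4 | 11.85 | 9.96 | 16% | 7.83/6.63 = 1.18 | 97.1% | 20.0% | 31.3% |

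The power losses are 0.9, 5.5 and 11.3 points.

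**Hand check.** If everyone missing leaves before Week 4, their imputed values carry essentially no interaction, so the estimate should be near (1 - 0.15) × 12 = 10.2. The simulation gives 9.96.

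**No true interaction, 15% missing.** The nominal 5% test rejects in 1.9% (spread) and 1.8% (early) of trials. With the subgroup variable in the imputation model it rejects in 3.5% and 4.7%.

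**Subgroup variable added, true interaction 12.** The means are 11.90, 12.24 and 11.85 (late, spread, early), and SE/SD is 1.00-1.01. The SE itself hardly moves (spread: 7.53 before, 7.57 after).

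**Other settings with spread dropout, 15% missing.** Shrinkage is 10% at correlation 0.3, and 12% if the effect builds over time.

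**Other missing fractions.** At 10% missing, shrinkage is about 2-10%. At 30% missing it is 5-32%, with SE/SD of 1.21-1.49.

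**Further simulations.** A second one at 15% missing and correlation 0.6 gave means of 10.4-11.3, SE/SD of 1.15-1.22 and power losses of about 8-11 points. A smaller one (270 trials, 15.5% missing at random, 3% intermittent gaps) fitted the unstructured MMRM itself. Imputation lowered the interaction by 0.83 relative to direct MMRM (0.83/12 = 7%), with SE 6.91 against SD 6.03. Direct MMRM reported 6.70 against 6.68.

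**The case against.** **The size is modest.** In the 270-trial run the shift of 0.83 is 0.83/6.91 = 0.12 of one standard error. The assumed interaction of 12 is as large as the whole planned treatment effect, and power for it is only about 40% even with complete data (40.6% in the spread scenario). This stands. The trial cannot settle these interactions under either method.

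**The shrunken estimate has the smaller mean squared error.** With spread dropout, root mean squared error is √(6.69² + 0.63²) = 6.72 under the SAP imputation and √(7.49² + 0.24²) = 7.49 with the subgroup variable added. This also stands for point estimation. It does not rescue the p-value, because the test uses a standard error that does not match the estimator.

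**The switch may not be reached.** The 15% is a sample-size assumption. Protocol 7.1 encourages subjects who stop investigational product to complete all visits, and Appendix 11 allows SNOT-22 at home. The point is therefore conditional, but SAP 3.3 itself expects missed assessments during the pandemic.

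**The strata already carry part of the eosinophil effect.** CRSsNP subjects need a screening count of at least 250 cells/µL, so low counts should fall mainly in CRSwNP. An independent 50:50 subgroup may overstate the effect for this variable.

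**Stronger readings that the documents do not support.** A reader might infer that the intervals are wrong and would be shorter if corrected. They are slightly conservative, and adding the variable leaves their width almost unchanged. A reader might also infer that identifying responders is the trial's main question. Protocol 9.1 states hypotheses only for SNOT-22 overall and NPS in the CRSwNP stratum, and no subgroup test is powered.

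**Conclusion.** The point holds, conditionally. If at least 10% of Week 16 changes are missing for an endpoint, the 8.4.2 interaction tests for the eight omitted variables are biased toward no heterogeneity.

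At 15% missing, shrinkage is about 2-16%, Rubin's SE is about 8-22% above the estimator's own SD, and coverage is about 97%. The power loss is roughly 5-11 points, falling to about 1 point when all dropout follows Week 12. These sizes rest on the assumed interaction, correlation, subgroup split and dropout timing, none of which the documents give. They were obtained for SNOT-22 with a two-level subgroup. NPS has only Week 8 between baseline and Week 16, so less may carry through; that is an inference and was not simulated.

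It would be wrong to extend this to the primary result. The overall treatment comparison is unaffected. Region and the 8.4.1 strata are also unaffected, provided that the convergence rule in 8.3.1.2 has not removed them from the imputation model. The split by baseline score is hardly affected.

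**What to change.** State in 8.4.2 that, for subgroup variables not already in the imputation model, one of two rules applies:

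- the subgroup variable is added to the within-arm imputation model for that analysis; or
- MMRM without MI (8.3.1.1) is used whatever the amount of missing data.

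Under the first rule, say what happens if the convergence provision in 8.3.1.2 would drop the subgroup variable, since that would bring the problem back. Falling back on the second rule is enough. Region and own-baseline subgroups need no change.

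The first rule costs extra imputation runs, one set per subgroup variable and endpoint. The second needs less programming: the MMRM without MI is already specified, although Table 1 lists it as a sensitivity analysis only for the overall endpoints and 8.4.2 has none of its own. It does mix methods across forest-plot rows, so a footnote is needed wherever a row differs from the overall row. SAP Section 1 labels analyses added beyond the plan as post hoc, so the rule belongs in the SAP text.
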